7.2.1 Extended safety follow-up

Given the potential risk for delayed immune-related toxicities, safety follow-up may be performed up to 90 days after the last dose of avelumab administration.

The extended safety follow-up beyond 30 days after last avelumab administration may be performed either via a site visit or via a telephone call with subsequent site visit requested in case any concerns noted during the telephone call.

7.2.2 Tumor assessment during post treatment follow up

For patients who have completed 12 months of treatment without progressive disease or discontinued treatment for reasons other than PD, the tumor assessments by cystoscopy and urine cytology should be repeated every 3 months for one year as per standard of care or until tumor progression.

7.3 Biological Sample Collection for Translational Study

We will assess immune profile in the pre- and post- treatment urine and blood as potential biomarkers that would associate with tumor response from the combination of avelumab and intravesical BCG. The analysis of other molecular profile may be optional if sample of cystoscopy and urine cytology is available.

7.3.1 Urine collection:

Urine will be collected before BCG treatment on the following days:

BCG Induction phase:

- Week 1 day 1 (Day 1, before BCG treatment)
- Week 4 day 1 (day 22, before BCG treatment)
- Week 7 day 1 (day 43)

BCG maintenance phase:

- Day 1 of Month 3 and 6 Maintenance: before BCG treatment

Urine specimen will be sent to the Stephenson Cancer Center biorepository for storage, which will be analyzed using a multiplexed immunoassay if collaborative funding is available.

7.3.2 Blood collection:

Blood sample for exploratory biomarkers will be collected before BCG treatment on the following days:

BCG Induction phase:

- Week 1 day 1 (Day 1, before BCG and avelumab treatment)

BCG maintenance phase:

- Day 1 of Month 3 and 6 Maintenance: before BCG and avelumab treatment

Blood specimen will be sent to the Stephenson Cancer Center biorepository for storage, which will be analyzed for immune profile changes if collaborative funding is available.

7.3.3 Sample shipping

Blood and urine samples will be sent to the Stephenson Cancer Center biorepository for processing and biomarker testing (See lab manual for detailed instructions).

8 EVALUATION CRITERIA

8.1 Safety Evaluation

Toxicity assessment is required prior to each BCG and/or avelumab treatment. Toxicity and grades will be classified using the NCI Common Terminology Criteria for Adverse Events (CTCAE) version 5.0. Dose limiting toxicity (DLT) will be monitored during the first 6 weeks of induction treatment with intravesical BCG and IV avelumab. Definition of DLT is described in [section 5.2.1](#).

Completion rate of induction therapy with combined BCG + avelumab is defined as completion of at least 5 of 6 treatments of each BCG and avelumab within 8 weeks during BCG induction phase.

Six-month treatment completion rate will be based on patients' completion of at least 2 of 3 BCG treatments within each 5 week period at the 6 Month maintenance treatment.

8.1.1 Definition of Evaluable patients for Safety Analysis

Evaluable patients will be defined as patients who receive at least one dose of intravesical BCG and avelumab.

8.2 Efficacy Evaluation

Cystoscopy and urine cytology will be obtained at screening and at Month 3, 6, 9, and 12. Only frankly malignant cytology will be considered positive and used to determine the need for bladder biopsy and further evaluation. Three-month complete response (CR) rate, 6-month CR rate, recurrence free survival (RFS), cystectomy-free survival (C

FS), and overall survival will be evaluated as the following.

Time to High-Grade Recurrence (TTHGR) is defined as time from date of first treatment to first high-grade recurrence. Patients without a recurrence will be censored at their last cystoscopy date. Those who die without a recurrence are also counted as a recurrence and high-grade recurrence at time of death.

Time to Recurrence (TTR) is identical to TTHGR with the addition that failure with any-grade bladder cancer is considered an event.

Progression-free survival (PFS) is defined as time from date of first treatment to first evidence of muscle invasive bladder cancer, metastatic disease, or death due to any cause. Those without an event are censored at their last valid tumor assessment, or at the last tumor assessment before patient start of the new therapy if a patient has started new anti-cancer therapy.

Complete Response: For the subset of patients with CIS (with or without concomitant Ta or T1 disease) at study entry, a 6-month biopsy is required. A negative biopsy at 6 months will provide evidence of complete response. A +/- 10 day window will be allowed around the disease assessment time point. Patients receiving a second induction will not be required to undergo 6-month biopsy

Duration of Complete Response: For the subset of patients with CIS (with or without concomitant Ta or T1 disease) at study entry who achieve a CR, duration is defined as time from first documentation of CR to time of first high grade recurrence. Patients who remain CR at end of study (EOS) are censored at their last cystoscopy date.

Overall survival (OS) is defined as the duration from the first dose date of the study drug until death due to any cause. Patients who are still alive at EOS are censored on the date they will be last known to be alive. An exploratory analysis to determine OS at EOS will be estimated by the Kaplan-Meier method.

Patient Reported Outcomes:

The EORTC QLQ-C30: is a 30-item cancer-specific quality of life questionnaire developed to assess QOL endpoints [33]. The measure consists of 5 functional scales (physical, role, cognitive, emotional and social), 3 symptom scales (fatigue, pain, and nausea/vomiting), a global health status / quality of life scale, and additional symptoms commonly reported by cancer patients (dyspnoea, loss of appetite, insomnia,

constipation and diarrhea) and perceived financial impact of the disease (<https://www.eortc.be/qol/files/SCManualQLQ-C30.pdf>). The EORTC QLQ-C30 is reliable and has discriminatory association with clinical status, disease stage, and symptom severity. Patients are asked to answer questions regarding their symptoms and/or quality of life on day 1 prior to BCG treatment during BCG induction phase and day 1 of BCG maintenance phase.

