2.2.2 Secondary Endpoints

- 6 Month maintenance treatment completion as defined as completion of at least 2 of 3 maintenance treatments within a 5-week period without unacceptable toxicities or disease progression. Disease status will be evaluated based on cystoscopy and urine cytology prior to maintenance therapy.

Patients with persistent or recurrent high-grade disease at 6 Month cystoscopy will be taken off treatment. Low-grade recurrence will be tolerated without treatment interruption.

- 3-month and 6-month complete response (CR) based on negative cystoscopy and urine cytology.
- Recurrence free survival (RFS) at 6 and 12 months, defined as proportion of patients who are alive and free of persistent or recurrent NMIBC based on cystoscopy, cytology and/or biopsy.
- Progression-free survival (PFS) at 6 and 12 months, as defined by time from day of first treatment to first progression to higher grade or stage, including muscle-invasive disease or death from any cause
- Cystectomy-free survival (CFS), defined as time from study initiation to cystectomy or death
- Overall survival, defined as time from day of first treatment to death from any cause

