3.1 Inclusion Criteria

1. Histologically or cytologically documented Non-muscle Invasive Bladder Cancer (NMIBC).
2. Patient with BCG-treated but unresponsive NMIBC (persistent or recurrent defined as tumor lesion present after prior response).
3. An Eastern Cooperative Oncology Group (ECOG) Performance Status score of 0 to 2.
4. Patients who are able to understand and sign the informed consent form.
5. Age \geq 18 years old
6. Ability to comply with protocol
7. Life expectancy $>/=$ 12 weeks
8. Adequate hematologic and end-organ function
 - ANC \geq 1500/ μ L (without granulocyte colony-stimulating factor support within 2 weeks prior to the first dose of study treatment)
 - Platelet count \geq 100,000/ μ L (without transfusion within 2 weeks prior to the first dose of study treatment)
 - Hemoglobin \geq 9.0 g/dL; Patients may be transfused or receive erythropoietic treatment, at least 7 days prior to the first dose of study treatment, to meet this criterion.

- AST and ALT $\leq 2.5 \times$ ULN.
- Serum bilirubin $\leq 1.5 \times$ ULN; Patients with known Gilbert disease who have serum bilirubin level $\leq 3 \times$ ULN may be enrolled.
- INR and aPTT $\leq 1.5 \times$ ULN; this applies only to patients who are not receiving therapeutic anticoagulation; patients receiving therapeutic anticoagulation should be on a stable dose.
- Creatinine clearance $>/= 30$ milliliters per minute (mL/min) (calculated using the Cockcroft-Gault formula)

9. For women of childbearing potential: Negative serum or urine pregnancy test at screening.
10. For both male and female subjects: agreement to remain abstinent (refrain from heterosexual intercourse) or use highly effective contraceptive methods that result in a failure rate of $<1\%$ per year during the treatment period and for at least 30 days after the last dose of study drug

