10.2 Analytic Plan

Only evaluable patients as defined in Section 8.1.1 will be included in the statistical analysis. The proportion of patients receiving a complete induction course (at least 5 of 6 treatments of each BCG and avelumab within eight weeks of starting treatment) at 3 months and at 6 months will be calculated and a 95% Wilson score confidence interval constructed for the completion rate.

The 3-month and/or 6-month complete response (CR) rates will be summarized as the proportion (and 95% CI) of patients with complete tumor response at month 3 or 6 of study treatment.

Kaplan-Meier curves will be generated for overall survival, duration of response, progression-free survival, cystectomy-free survival, time to recurrence, and time to high-grade recurrence. Median survival time and 95% confidence intervals will be calculated. The EORTC QLQ-C30 questionnaire functional scales, symptom scales, and global health and quality of life scale will be summarized.

Frequency and severity of adverse events will be tabulated by body system, type and maximum grade. Serious adverse events will be listed.

Interim analysis

An interim safety analysis will be conducted when 3~6 patients have received ≥ 5 doses of BCG treatment in dose level 1. If the combination therapy in dose level 1 is not tolerated (2 or more patients experience a DLT), dose level -1 will be evaluated in additional 3~6 eligible patients. The decision rule is fully described in Section 5.2 Overall Study Design.

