- e. Overall survival (OS) is defined as time in months from first dose of the drug to the date of death. Patients who are still alive at EOS are censored on the date they were last known to be alive. Survival curve for OS will be generated using the Kaplan-Meier method. Median OS with 95% CI will be computed. If overall survival cannot be calculated due to no patient deaths, it will not be reported.
- f. Recurrence free survival (RFS) at 6 and 12 months, defined as proportion of patients who are alive and free of persistent or recurrent NMIBC based on cystoscopy, cytology and/or biopsy. Survival curve for RFS will be generated using the Kaplan-Meier method. Median PFS with 95% CI will be computed. Patients without a recurrence will be censored at their last cystoscopy date.
- g. Cystectomy-free survival (CFS), defined as time from study initiation to cystectomy or death. Survival curve for CFS will be generated using the Kaplan-Meier method. Median PFS with 95% CI will be computed. If CFS cannot be calculated due to not enough patients undergoing cystectomy, it will not be reported.

9. Safety Analyses

a. Adverse Events

- i. Severity of AEs will be graded according to the CTCAE Version 5.0. Adverse events not included in the CTCAE, Version 5.0 must be graded as follows: Mild, Moderate, Severe, Life-threatening, and Fatal according to the following definitions:
 1. Mild: The AE is noticeable to the patient but does not interfere with routine activity.
 2. Moderate: The AE interferes with routine activity but responds to symptomatic therapy or rest.
 3. Severe: The AE significantly limits the patient's ability to perform routine activities despite symptomatic therapy.
 4. Life-threatening: The AE places the patient at risk of death at the time of the event.
 5. Fatal: The AE results in the death of the patient.
- ii. Frequency and severity of adverse events will be tabulated by body system, type and maximum grade. Serious adverse events will be listed.

b. Laboratory Abnormalities

- i. An abnormal laboratory value that is not already associated with an AE is to be recorded as an AE only if any one of the following criteria is met:
 1. an action on the study drug is made as a result of the abnormality
 2. intervention for management of the abnormality is required
 3. at the discretion of the investigator should the abnormality be deemed clinically significant

10. Handling of Missing Data

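### SAP 8.f's censoring sentence contradicts its own definition of recurrence-free survival, and Protocol 8.2 gives time to high-grade recurrence no event for disease that never clears

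*Protocol*

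**What the plan says.** **TTHGR.** Protocol 8.2 states that it "is defined as time from date of first treatment to first high-grade recurrence. Patients without a recurrence will be censored at their last cystoscopy date". It adds one further event: "Those who die without a recurrence are also counted as a recurrence and high-grade recurrence at time of death". Persistent disease is not mentioned.

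**TTR.** Protocol 8.2: "Time to Recurrence (TTR) is identical to TTHGR with the addition that failure with any-grade bladder cancer is considered an event". The word used there for the event is broader than recurrence and is not defined.

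**RFS.** Protocol 2.2.2 and SAP 2.b.iii and 8.f define RFS at 6 and 12 months as the share of patients who are living with neither persisting nor recurring NMIBC. SAP 8.f also asks for a Kaplan-Meier curve and gives this censoring rule: "Patients without a recurrence will be censored at their last cystoscopy date".

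**Persistence elsewhere.** Protocol 3.1, item 2, describes the entry population as "persistent or recurrent defined as tumor lesion present after prior response". Protocol 2.2.2 says "Patients with persistent or recurrent high-grade disease at 6 Month cystoscopy will be taken off treatment". Protocol 6.3.2 allows a repeat induction for patients whose disease persists at the Month 3 cystoscopy, provided it has not progressed.

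**Where the curves are planned.** Protocol 10.2 lists "time to recurrence, and time to high-grade recurrence" among its Kaplan-Meier curves but not RFS. The SAP plans an RFS curve but has no item for TTHGR or TTR.

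**The concern.** A patient whose high-grade tumour is still present at Month 3 and Month 6 has failed treatment, but has not recurred in the ordinary sense because the disease never went away. If the censoring sentences are applied as written, that patient leaves the risk set at the last cystoscopy with no event. Kaplan-Meier estimation then treats the patient as having the same future risk as those who are still disease-free. That assumption is false here: the patient is censored with the failure already on record. The censoring is informative, and its direction is known. The curve is too high, and the error generally grows as more patients fail to clear.

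At stake are the TTHGR and RFS curves and their medians, and possibly TTR. Two programmers working from SAP 8.f could produce different RFS curves, one following the definition and the other the censoring sentence. If the choice were made after the data were seen, it could move the 12-month figure materially.

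**Working it through.** **1. Plan's own figure.** None is given for TTHGR, TTR or RFS. The only precision figure in the documents is the Wilson lower limit for Month 6 completion (60%, n = 18). It reproduces at 37.6% and has no bearing on this point.

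**2. The texts side by side, for a patient with high-grade disease that never clears.**

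| Measure | Events in the text | Literal handling |
|---|---|---|
| TTHGR (Protocol 8.2) | High-grade recurrence; death | Censored at last cystoscopy |
| TTR (Protocol 8.2) | As TTHGR, plus undefined failure of any grade | Unclear |
| RFS definition (Protocol 2.2.2, SAP 8.f) | Persistent disease, recurrent disease, or death | Failure |
| RFS curve (SAP 8.f) | Censoring sentence names recurrence only | Censored |

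The last two rows cannot both be followed.

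**3. Illustration of size.** Inputs: n = 18 is from Protocol 10.1. Everything else is assumed: k patients with persistent high-grade disease from Month 3; r recurrences among the other n − k, taken as about 30% rounded to whole patients and placed in turn at Months 6, 9 and 12; no deaths; no other censoring before Month 12.

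Formulas for the 12-month estimate:

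- Persistence counted as an event at Month 3: (n − k − r)/n.
- Persistence censored at Month 3: (n − k − r)/(n − k).
- Persistence censored at Month 6, with e recurrences at Month 6 counted before the censoring: [(n − e)/n] × [(n − k − r)/(n − k − e)].

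For k = 4, r = 4 (two recurrences at Month 6, one at Month 9, one at Month 12):

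- Counted: 14/18 × 12/14 × 11/12 × 10/11 = 10/18 = 55.6%.
- Censored at Month 3: 12/14 × 11/12 × 10/11 = 10/14 = 71.4%.
- Censored at Month 6: 16/18 × 11/12 × 10/11 = 74.1%.

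| k | r | Counted | Censored at Month 3 | Censored at Month 6 |
|---|---|---|---|---|
| 4 | 4 | 55.6% | 71.4% | 74.1% |
| 7 | 3 | 44.4% | 72.7% | 75.6% |
| 9 | 3 | 33.3% | 66.7% | 70.8% |
| 11 | 2 | 27.8% | 71.4% | 78.7% |
| 14 | 1 | 16.7% | 75.0% | 94.4% |

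The gap runs from about 16 points (71.4 − 55.6) to about 78 points (94.4 − 16.7). The last row leaves 4 of 18 (22%) clearing, close to the response of around 20% that Protocol 1.2 cites for repeat BCG in disease refractory to the first induction. That figure is for BCG without avelumab, so the row is an outer case and not a forecast.

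**4. Medians.** With k = 7 and persistence counted, the curve falls to 11/18, 10/18, 9/18 and 8/18 at Months 3, 6, 9 and 12, so it reaches 50% at Month 9. With persistence censored at Month 3 it never falls below 72.7%, and the median is not reached.

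**5. Limiting case.** With no recurrences or deaths, the literal curve stays at 100% throughout. The disease-free share is then 14/18 = 77.8% for k = 4 and 4/18 = 22.2% for k = 14.

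**6. Check against the stated definition.** In these scenarios the counted column equals the simple proportion alive and disease-free at 12 months, which is how the documents define RFS at that time.

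**The case against.** The strongest reply is that the authors use recurrence loosely for any treatment failure. TTR is said to be the same as TTHGR apart from the grade of disease, and its event is called failure. On that reading TTHGR already means failure with high-grade disease and includes persistence. Inclusion criterion 2 describes disease before entry, not an on-study event, and its parenthesis can be taken as defining both words together. A statistician who starts from the RFS definition would count persistent disease as failure whatever the censoring sentence says. The analyses are secondary or descriptive, no dose or stopping decision depends on them, and persistence will show in the 3- and 6-month complete response rates.

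Much of this stands. The loose reading is possible, which is why TTR is called ambiguous here. Inclusion criterion 2 is weak support alone. But Protocol 2.2.2 names persistent and recurrent disease together when both are meant, and Protocol 6.3.2 gives persistence its own pathway. The TTHGR rule and the SAP censoring sentence name only recurrence. A plan should not rely on the analyst to choose the charitable reading.

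Some stronger inferences are not supported:

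- *That only recurrence counts and everyone else is censored.* Death without recurrence is an event in TTHGR and TTR, and RFS requires the patient to be alive.
- *That the plan makes persistent disease an RFS success.* Its definition makes it a failure. The fault is a conflict between that definition and the censoring sentence.
- *That these patients are carried event-free to Month 12.* They leave the risk set at their last cystoscopy.
- *That Month 3 persistence must be an event even if re-induction clears it, or that the 6-month RFS proportion is wrong to count such a patient as disease-free.* The proportion is a landmark measure and is coherent as defined. Either change would redefine the endpoint.

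**Conclusion.** Wrong as written, of moderate severity. SAP 8.f contradicts itself on persistent disease. Protocol 8.2 gives TTHGR no event for high-grade disease that never clears and leaves TTR unclear. Followed literally, the censoring sentences bias the curves upward.

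The direction is certain on that reading, but the size is not. It depends on how many patients fail to clear, how many of the others recur, and when the persistent patients had their last cystoscopy, and the documents give none of these. The gap of about 16 points for 4 persistent patients of 18 is an illustration, and the wider range shows only how it moves with the assumptions. The primary endpoint, completion of induction, is not touched.

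**What to change.** 1. **SAP 8.f.** Censor only patients who are alive with neither persistent nor recurrent disease, at their last cystoscopy. The curve then matches the definition in the same item.
2. **Protocol 8.2.** State that never-cleared disease is an event: high-grade for TTHGR, any grade for TTR.
3. **Event date.** Prespecify one date for persistence, including for patients who receive the permitted repeat induction after Month 3. Two choices are defensible: the first positive on-study assessment, or the assessment after re-induction. Name one as the main analysis and the other as a sensitivity analysis, and use the same rule in SAP 8.f. If the first positive assessment is chosen, note that the RFS curve and the landmark proportion can differ for a patient who clears after re-induction.
4. **RFS at 6 and 12 months.** Keep these proportions as defined.

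The cost is a wording change in both documents and one added sensitivity analysis. No visits, data items or patients are added. The drawback is that the reported curves will look less favourable than under the literal rule.
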